2. OBJECTIVES AND ENDPOINTS

2.1 Objectives

Primary Objective: To assess the safety and tolerability of two multiple oral YPL-001 dose levels versus placebo in moderate to severe chronic obstructive pulmonary disease (COPD) patients.

Secondary Objective: To assess the number and magnitude of daily respiratory symptoms of two multiple oral YPL-001 dose levels versus placebo in moderate to severe COPD patients.

Exploratory Objectives: To evaluate the following in moderate to severe COPD patients:

1. To assess BAL epithelial brushings for YPL-001 component levels.
2. To compare BAL samples for total cell count (cells/mL) macrophages, lymphocytes, neutrophils, and eosinophils as a percentage of total cells; neutrophil, macrophage, lymphocyte, and eosinophil counts as absolute inflammatory cell numbers in YPL-001 groups versus placebo group.
3. To compare BAL samples for TNF- α , IL-1 β , IL-4, IL-5, IL-6, IL-8, IL-13, MPO, neutrophil elastase, MCP-1, and MMP-9 in YPL-001 groups versus placebo group.
4. To compare blood inflammatory markers (total and differential cell counts as absolute and percentage for neutrophils, monocytes, eosinophils and lymphocytes) and concentrations of CRP, fibrinogen, TNF- α , IL-1 β , IL-4, IL-5, IL-6, IL-8, IL-13, MCP-1, and MMP-9 in YPL-001 groups versus placebo group.
5. To compare spirometric functions (FEV₁, FVC, FEV₁/FVC, and IC) in YPL-001 groups versus placebo group.

6. To compare patient reported outcomes (BDI/TDI, CAT) in YPL-001 groups versus placebo group.
7. To assess verproside and picroside II concentration in plasma and BAL and verproside and picroside II PK in plasma following multiple oral doses administration of two YPL-001 dose levels.

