3. STUDY DESIGN

This is a Phase 2a, proof-of-concept, multicenter, randomized, double-blind, double-dummy, 3-treatment, parallel study, with low and high YPL-001 doses (80 mg and 160 mg twice daily [BID]) and a placebo control, in moderate to severe COPD male and female patients.

Sixty (60) patients will be enrolled and randomized into 3 treatment groups (20 patients per group). Patients will participate only once. An approximately equal number of current and ex-smokers will be enrolled in the study.

Screening of patients will occur within 14 days of Day 1 (inclusive) of the Run-in Period.

Following screening, eligible patients will discontinue non-permitted respiratory drugs and enter a 14 ± 2 days Run-in Period during which patients will be given albuterol taken on an as required basis and daily tiotropium 18 μ g to be administered at home. They will record their daily symptoms in an electronic diary (e-diary) throughout the Run-in Period.

Patients will return to the clinical research unit (CRU) in the morning of Day -3 to -1 for Check-in of the Treatment Period to confirm their eligibility and undergo Check-in scheduled study procedures. Patients will return to the CRU on the morning of Day 1 to be randomized and receive one of the 3 treatments and undergo all scheduled study procedures. Patients will return on the morning of Days 15 (± 2 days), 29 (± 2 days), 43 (± 2 days), 54 (± 1 day), and 56 of the Treatment Period for study drug administration and procedures. Prior to each release from the CRU, patients will receive sufficient doses to be self-administered at home until the next morning visit at the CRU. Patients will continue recording their daily symptoms via the e-diary throughout the Treatment Period.

YLP-001 and placebo will be administered approximately every 12 hours under fasting conditions.

Patients will remain ambulatory or seated upright for 1 hour following each study medication administration.

Safety and tolerability will be assessed throughout the study through physical examinations, vital signs, pulse oximetry, electrocardiograms (ECGs), clinical laboratory tests, and adverse events (AEs).

Assessment of respiratory symptoms and symptom burden in YPL-001 and placebo treatments will be performed daily through patient self-report of PEF, major and minor symptoms of COPD exacerbation, dyspnea, and activity.

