7.1.1.3 Pulmonary Function Biomarkers

Spirometry measures for assessment of the pulmonary function will be taken pre- and post-bronchodilator (albuterol) administration at Screening (baseline), at Check-in, on Days 15 (± 2), 29 (± 2), 43 (± 2), and 55 or 56 (predose) of the Treatment Period, and prior to early termination, if applicable.

Pulmonary function measurements include the following parameters below:

- FEV1;
- FVC;
- FEV1/FVC;
- IC.

Short and long acting β 2-agonist and anticholinergic bronchodilators agents will be withheld approximately 4 and 24 hours, respectively, before each pre-bronchodilator spirometry.

At screening, baseline pre-bronchodilator spirometry will be performed (prior to albuterol administration) for a minimum of 3 times and a maximum of 8 times in order to obtain 3 manoeuvres with FEV1 values within 150 mL of each other, using the manoeuvre with the highest value of FEV1 and FVC as the basis for comparison.

Patients shall receive 4 inhalations of albuterol, (100 μ g/inhalation), for a total dose of 400 μ g via metered-dose inhaler using a spacer. Within approximately 20 to 30 minutes after albuterol administration, the baseline post-bronchodilator spirometry will be performed.

Assessment of FEV1 stability will take place:

1. Prior to Day 1 dosing of the Treatment Period (Check-in measurement): Predose FEV1 is defined as the time-point prior to Day 1 dosing in the Treatment Period and will be performed pre- and post-bronchodilator administration. Predose FEV1 will be compared to the corresponding baseline measurement. If the best FEV1 measurement at predose at Check-in of the Treatment Period has declined by greater than 20% from the best FEV1 at screening, the visit may be rescheduled up to 3 times, at the discretion of the Investigator.
2. Following Day 1 dosing: At all other spirometry time point, measurements will be performed once. If the value shows a difference of greater than 150 mL

decline than the best FEV1 value collected predose at Check-in, up to 3 measures will be performed.

Consideration should be given, if a patient experiences any change in post Day 1 dose FEV1 from the Day 1 predose FEV1 value (measured following dosing with albuterol) equal to or greater than 20 % and should alert the PI to consider whether individual patients should continue to dose.

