7.1.2 Data Summarization and Presentation

Descriptive statistics will be generated using SAS[®] Version 9.3 (or higher) for the actual values (raw) and relative values (% change from baseline or total) as specified above for each type of biomarker variable. When applicable, the PD biomarkers (BAL, blood, pulmonary function) will be summarized by treatment group and time point using descriptive statistics including sample size (N), arithmetic mean, standard deviation (SD), coefficient of variation (CV%), median, minimum, and maximum.

Figures will be created to display mean measure, level or activity value as a function of time on linear plots with and without SD, as appropriate.

The quality of life parameters reported from the BDI/TDI and CAT questionnaires will be listed and presented descriptively using SAS® Version 9.3 (or higher)

Additional analysis may be performed if deemed appropriate.

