	P-Value (Between)		X.XXX		X.XXX		
Pre^ 15+/-2	N	XX	XX	XX	XX	XX	XX
	Mean	XX.X	-X.X	XX.X	-X.X	XX.X	-X.X
	SD	XX.XX	XX.XX	XX.XX	XX.XX	XX.XX	XX.XX
	CV%	XX.X	XX.X	XX.X	XX.X	XX.X	XX.X
	Median	XX.X	-X.X	XX.X	-X.X	XX.X	-X.X
	Minimum	XX	-XX	XX	-XX	XX	-XX
	Maximum	XX	XX	XX	XX	XX	XX
	P-Value (Within)		X.XXX		X.XXX		X.XXX
	P-Value (Between)		X.XXX		X.XXX		
Post^	N	XX	XX	XX	XX	XX	XX
	Mean	XX.X	-X.X	XX.X	-X.X	XX.X	-X.X
	SD	XX.XX	XX.XX	XX.XX	XX.XX	XX.XX	XX.XX
	CV%	XX.X	XX.X	XX.X	XX.X	XX.X	XX.X
	Median	XX.X	-X.X	XX.X	-X.X	XX.X	-X.X
	Minimum	XX	-XX	XX	-XX	XX	-XX
	Maximum	XX	XX	XX	XX	XX	XX
	P-Value (Within)		X.XXX		X.XXX		X.XXX
	P-Value (Between)		X.XXX		X.XXX		
Change^	N	XX	XX	XX	XX	XX	XX
	Mean	XX.X	-X.X	XX.X	-X.X	XX.X	-X.X

Yungjin Pharm. CO., LTD.

YPL-001, Project Number YPL-001-YJP-130403

Celerion, Clinical Study Report No. AA98497

SD	XX.XX	XX.XX	XX.XX	XX.XX	XX.XX	XX.XX
CV%	XX.X	XX.X	XX.X	XX.X	XX.X	XX.X
Median	XX.X	-X.X	XX.X	-X.X	XX.X	-X.X
Minimum	XX	-XX	XX	-XX	XX	-XX
Maximum	XX	XX	XX	XX	XX	XX
P-Value (Within)		X.XXX		X.XXX		X.XXX
P-Value (Between)		X.XXX		X.XXX		X.XXX

< > < > < >

FEV1 = forced expiratory volume in one second, FVC = forced vital capacity, IC = inspiratory capacity

^ Pre- and Post-Bronchodilator, Change = Post- minus Pre-

Baseline is screening measurement.

P-value (Within) came from Wilcoxon Signed Rank Test, P-value (Between) came from Wilcoxon Rank Sum Test: A vs C and B vs C

Treatment A: Multiple oral doses of YPL-001 80 mg BID on Days 1 - 55

Treatment B: Multiple oral doses of YPL-001 160 mg BID on Days 1 - 55

Treatment C: Multiple oral doses of placebo BID on Days 1 - 55

Note: Patients following up to Amendment version 5 of the protocol also received a morning dose on Day 56.

Programmers note:

Measurements to include are FEV1 (L), FVC (L), FEV1/FVC (%), and IC (L).

Postdose time points are Day 15+/-2, 29+/-2, 43+/-2, and 55 or 56.

If space is limiting, Day "55 or 56" may be presented as "56" with a footnote indicating "Day 55 or 56".

Program: /AAXXXX/XXX/sas_prg/stsas/lis_PROGRAMNAME.sas DDMMYYYY HH:MM

Quality of Life

Page X of X

Table 14.2.2.10 Categorical Summary of Baseline Dyspnea Index (BDI) at Check-in by Treatment Assignment of Multiple Oral YPL-001 Doses of 80 mg and 160 mg and Placebo in COPD Patients (Treatments A - C)

Treat- ment	N						Amount Uncertain	Unknown	Impaired for Reasons Other than Shortness of Breath
		Grade 4	Grade 3	Grade 2	Grade 1	Grade 0			

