	C	Functional Impairment	XX	XX (XX%)	XX (XX%)	XX (XX%)	X (X%)	XX (XX%)	XX (XX%)	XX (XX%)	XX (XX%)
		Magnitude of Task	XX	X (XX%)	X (XX%)	X (XX%)	X (X%)	X (XX%)	X (XX%)	X (XX%)	X (XX%)
		Magnitude of Effort	XX	X (XX%)	X (XX%)	X (XX%)	X (XX%)	X (XX%)	X (XX%)	X (XX%)	X (XX%)

-3 = Major Deterioration, -2 = Moderate Deterioration, -1 = Minor Deterioration, 0 = No Change, +1 = Minor Improvement, +2 = Moderate Improvement, +3 = Major Improvement

Treatment A: Multiple oral doses of YPL-001 80 mg BID on Days 1 - 55

Treatment B: Multiple oral doses of YPL-001 160 mg BID on Days 1 - 55

Treatment C: Multiple oral doses of placebo BID on Days 1 - 55

Note: Patients following up to Amendment version 5 of the protocol also received a morning dose on Day 56.

Programmers note:

Time points are Day 15+/-2, 29+/-2, 43+/-2, and 54+/-1 or 56.

If space is limiting, Day "54+/-1 or 56" may be presented as Day "54" with a footnote indicating this is "Day 54+/-1 or 56".

Program : /AAXXXX/ECR/sas_prg/stsas/tab/PROGRAMNAME.sas DDMMYYYY HH:MM

Table 14.2.2.12 Change From Baseline of Combined Focal Score (-9 - +9) from Transition Dyspnea Index (TDI) Following Multiple Oral YPL-001 Doses of 80 mg and 160 mg and Placebo in COPD Patients (Treatments A - C)

Day	Summary Statistic	Treatment A		Treatment B		Treatment C	
		(N = XX)	(N = XX)	(N = XX)	(N = XX)	(N = XX)	(N = XX)
15+/-2	N	XX		XX		XX	
	Mean	-X.X		-X.X		-X.X	
	SD	XX.XX		XX.XX		XX.XX	
	CV%	XX.X		XX.X		XX.X	
	Median	-X.X		-X.X		-X.X	
	Minimum	-XX		-XX		-XX	
	Maximum	XX		XX		XX	
	P-Value (Between)	X.XXX		X.XXX			
29+/-2	N	XX		XX		XX	
	Mean	-X.X		-X.X		-X.X	
	SD	XX.XX		XX.XX		XX.XX	
	CV%	XX.X		XX.X		XX.X	
	Median	-X.X		-X.X		-X.X	
	Minimum	-XX		-XX		-XX	
	Maximum	XX		XX		XX	
	P-Value (Between)	X.XXX		X.XXX			

TDI has 3 domains (functional impairment, magnitude of task, and magnitude of effort).

The change from baseline is measured by the TDI score which ranges from -3 (major deterioration) to +3 (major improvement) for each domain with the TDI focal score consisting in the sum of each domain (-9 to +9).

P-value (Between) came from Wilcoxon Rank Sum Test: A vs C and B vs C

Treatment A: Multiple oral doses of YPL-001 80 mg BID on Days 1 - 55

Treatment B: Multiple oral doses of YPL-001 160 mg BID on Days 1 - 55

Treatment C: Multiple oral doses of placebo BID on Days 1 - 55

Note: Patients following up to Amendment version 5 of the protocol also received a morning dose on Day 56.

Programmers note:

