Level of Energy: 0 = I have lots of energy, 5 = I have no energy at all

Treatment A: Multiple oral doses of YPL-001 80 mg BID on Days 1 - 55

Treatment B: Multiple oral doses of YPL-001 160 mg BID on Days 1 - 55

Treatment C: Multiple oral doses of placebo BID on Days 1 - 55

Note: Patients following up to Amendment version 5 of the protocol also received a morning dose on Day 56.

Program : /AAXXXX/ECR/sas_prg/stsas/tab/PROGRAMNAME.sas DDMMYY YYYY HH:MM

Table 14.2.2.17 Summary and Change From Baseline of Individual Score (0 - 5) and Total Score (0 - 40) from Chronic Obstructive Pulmonary Disease (COPD) Assessment Test (CAT) Following Multiple Oral YPL-001 Doses of 80 mg and 160 mg and Placebo in COPD Patients (Treatments A - C)

CAT Item	Day	Summary Statistic	Treatment A		Treatment B		Treatment C	
			Result	Change From Baseline	Result	Change From Baseline	Result	Change From Baseline
			(N = XX)	(N = XX)	(N = XX)	(N = XX)	(N = XX)	(N = XX)
Cough	Check-in	N	XX		XX		XX	
		Mean	XX.X		XX.X		XX.X	
		SD	XX.XX		XX.XX		XX.XX	
		CV%	XX.X		XX.X		XX.X	
		Median	XX.X		XX.X		XX.X	
		Minimum	XX		XX		XX	
		Maximum	XX		XX		XX	
15+/-2		N	XX	XX	XX	XX	XX	XX
		Mean	XX.X	-X.X	XX.X	-X.X	XX.X	-X.X
		SD	XX.XX	XX.XX	XX.XX	XX.XX	XX.XX	XX.XX
		CV%	XX.X	XX.X	XX.X	XX.X	XX.X	XX.X
		Median	XX.X	-X.X	XX.X	-X.X	XX.X	-X.X
		Minimum	XX	-XX	XX	-XX	XX	-XX
		Maximum	XX	XX	XX	XX	XX	XX
		P-Value (Within)		X.XXX		X.XXX		X.XXX
		P-Value (Between)		X.XXX		X.XXX		X.XXX

Baseline is Check-in measurement.

P-value (Within) came from Wilcoxon Signed Rank Test, P-value (Between) came from Wilcoxon Rank Sum Test: A vs C and B vs C

Treatment A: Multiple oral doses of YPL-001 80 mg BID on Days 1 - 55

Treatment B: Multiple oral doses of YPL-001 160 mg BID on Days 1 - 55

Treatment C: Multiple oral doses of placebo BID on Days 1 - 55

Note: Patients following up to Amendment version 5 of the protocol also received a morning dose on Day 56.

Programmers note: CAT items are Cough, Mucus Production, Chest Tightness, Breathlessness, Activities, Confidence, Sleepiness, Energy, and Total score.

For the "Day 54+1 or Day 56" time point (if space is limiting), this may be presented as Day "54" with a footnote indicating this is "Day 54+1 or 56".

Program : /AAXXXX/ECR/sas_prg/stsas/tab/PROGRAMNAME.sas DDMMYYYY HH:MM

Pharmacokinetics

Note: Tables 14.2.4.1.1 - 2, 14.2.4.2.1 – 2 (plasma), 14.2.4.3.1, and 14.2.4.4.1 (epithelial brushing) will be in a similar format:

Page X of X

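### Spirometry, CAT and TDI are compared with placebo only by visit-by-visit rank-sum p-values, with no prespecified between-arm estimate, confidence interval or baseline adjustment

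*SAP*

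**What the plan says.** Section 2.1 words both objectives as comparisons. Objective 5 covers FEV1, FVC, FEV1/FVC and IC "in YPL-001 groups versus placebo group". Objective 6 is "To compare patient reported outcomes (BDI/TDI, CAT) in YPL-001 groups versus placebo group".

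Section 7.1.2 gives the analysis. Pulmonary function is summarised by arm and time point with descriptive statistics. The BDI/TDI and CAT results "will be listed and presented descriptively using SAS® Version 9.3 (or higher"). The section adds that further analysis may be done if thought appropriate, without saying what.

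Inference appears only in the shells of Section 12.2. For CAT (Table 14.2.2.17) and spirometry (Table 14.2.2.7, whose format Tables 14.2.2.8 and 14.2.2.9 share) the footnote reads "P-value (Within) came from Wilcoxon Signed Rank Test, P-value (Between) came from Wilcoxon Rank Sum Test: A vs C and B vs C". For the TDI focal score (Table 14.2.2.12) it reads "P-value (Between) came from Wilcoxon Rank Sum Test: A vs C and B vs C". Each visit is tested separately. The spirometry shell prints these p-values at Check-in as well as at the postdose visits.

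In-text Tables 11-8, 11-9 and 11-10, which carry these results into the report, show mean, SD and N per arm and no comparison.

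**The concern.** In a proof-of-concept trial of this size the useful product of a placebo comparison is an estimated difference and its range. A p-value alone does not tell a sponsor whether a non-significant result reflects no effect or an effect too imprecisely measured to see. The SAP does plan estimation elsewhere: Section 8.7 specifies a geometric mean ratio with a 90% CI for the 160 mg versus 80 mg pharmacokinetic comparison. It plans nothing of the kind for its placebo comparisons on these endpoints.

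The baselines needed for a sharper analysis are already collected: spirometry at Screening and Check-in, CAT at Check-in and BDI at Check-in. Subtracting baseline is not the same as adjusting for it. An unadjusted change score is noisier unless baseline and follow-up are very highly correlated, and a chance baseline imbalance between arms passes into the change through regression to the mean.

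**Working it through.** **Inputs from the SAP.** Section 3: "Sixty (60) patients will be enrolled and randomized into 3 treatment groups (20 patients per group"). Section 12.2: four spirometry parameters, each shown pre-bronchodilator, post-bronchodilator and as their difference; five tested time points (Check-in and four postdose visits); two contrasts; eight CAT items plus the total at four visits; TDI at four visits. The SAP states no effect size, SD, alpha or power for these endpoints, so there is no planned figure to reproduce.

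**Assumptions not in the SAP.** Equal SD at baseline and follow-up, correlation rho from 0.3 to 0.9, normal data, two-sided alpha 0.05 and no dropout.

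**Step 1: what is printed.**
- Spirometry: 4 x 3 x 5 x 2 = 120 between-arm p-values per table, 360 over three tables.
- CAT: 9 x 4 x 2 = 72.
- TDI: 4 x 2 = 8.
- Total: 440, none with a difference or interval beside it. The count describes the layout and does not measure the loss.
- At Check-in: 4 x 3 x 2 = 24 per spirometry table, 72 over three. Section 3 puts Check-in on Day -3 to -1 and randomisation on Day 1, so these test differences that treatment cannot have caused.

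**Step 2: precision, spirometry and CAT.** With outcome SD sigma at both times:
- variance of the change score = 2 sigma²(1 - rho);
- variance of follow-up after adjusting for baseline = sigma²(1 - rho²);
- ratio = (1 - rho²) / [2(1 - rho)] = (1 + rho)/2.

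| rho | adjusted / change-score variance | patients per arm giving the same precision if adjusted (20 x ratio) |
|---|---|---|
| 0.3 | 0.65 | 13 |
| 0.5 | 0.75 | 15 |
| 0.7 | 0.85 | 17 |
| 0.8 | 0.90 | 18 |
| 0.9 | 0.95 | 19 |

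The table ignores the small cost of estimating the baseline slope, roughly 1/37 (2.7%) of the variance with two arms of 20.

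**Step 3: simulation of the planned test.** Rank-sum on change against ANCOVA, 20 per arm, true effect 0.6 SD of the outcome, 5,000 runs per setting:

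| rho | power, rank-sum on change | power, ANCOVA |
|---|---|---|
| 0.3 | 33% | 47% |
| 0.5 | 45% | 57% |
| 0.7 | 64% | 72% |
| 0.9 | 98% | 98.5% |

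With no effect (3,000 runs), the rank-sum test rejected in 4.7% to 5.4% of runs, so it holds its level.

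**Step 4: TDI.** Under Section 7.1.1.4 the TDI is a direct rating of change from the BDI state, on its own scale from -9 to +9, while the BDI runs from 0 to 12. It is not follow-up minus baseline on one scale, so the Step 2 formula does not apply and no gain is quantified. The point for the TDI is only that the BDI is available as a covariate and is not used.

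**Step 5: which spirometry baseline.** Section 7.1.1.3, Table 11-8 and Table 14.2.2.7 take Screening as baseline. The listing shell for Appendix 16.2.6.2.25 takes Check-in. Section 3 places the tiotropium run-in between the two, so they are not interchangeable.

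**The case against.** The strongest defence is that these are exploratory objectives in a 60-patient Phase 2a trial whose primary objective is safety, and that a Wilcoxon test is a legitimate, robust choice. The test is indeed valid, and preferring a model to it is partly a matter of taste. That does not supply the missing estimate.

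A reader might infer that the plan gives no interpretable answer at all. The SAP does not support that. The shells tabulate N, mean and SD of change (or of the TDI score) per arm and visit, so an unadjusted difference and t-interval can be worked out by hand. What is missing is a prespecified, displayed and baseline-adjusted estimate.

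A reader might also infer that the baseline data are wasted. For spirometry and CAT they are not: the change score uses them, less efficiently than adjustment would. Only the BDI is left out of its comparison.

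Nor does the plan discard patients who leave early, since they contribute to each visit attended. Spirometry is also taken "and prior to early termination, if applicable", whereas the shell's note reads "Postdose time points are Day 15+/-2, 29+/-2, 43+/-2, and 55 or 56". How to use those values is a separate choice, and this point does not rest on it.

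The allowance for additional analysis in Section 7.1.2 commits to nothing and does not meet the point.

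**Conclusion.** The point holds as a worthwhile improvement, not as an invalid analysis. For spirometry, CAT and TDI, the only prespecified comparison with placebo is a by-visit rank-sum p-value, with no between-arm estimate, no confidence interval and no baseline covariate.

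For spirometry and CAT the cost is 10% to 25% of the change-score variance at rho 0.8 down to 0.5, and about 5% at 0.9. These figures assume equal SDs at both times; the correlations are assumed because the SAP gives none. The power figures further assume normal data, a 0.6 SD effect and complete follow-up, and individual 0-to-5 CAT items may depart from normality. No size is claimed for the TDI.

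The between-arm spirometry tests at Check-in serve no purpose under any of these assumptions.

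**What to change.** - In Section 7.1.2, prespecify one baseline-adjusted analysis for FEV1, FVC, FEV1/FVC, IC, CAT total and TDI focal score: either ANCOVA at the final visit, or a repeated-measures model with treatment, visit, treatment-by-visit and baseline. If the latter, name the covariance structure and degrees-of-freedom method.
- Use the Check-in score as covariate for CAT and the BDI focal score for the TDI. For spirometry, state one pre-randomisation baseline after reconciling Section 7.1.1.3 and Table 14.2.2.7 (Screening) with Appendix 16.2.6.2.25 (Check-in).
- Report A-C and B-C differences with 95% CIs at Day 55/56 for spirometry and Day 54/56 for CAT and TDI, and add them to Tables 11-8, 11-9 and 11-10.
- Keep the Wilcoxon test as a prespecified sensitivity analysis, with no switch of method after the data are seen.
- Delete the between-arm tests at Check-in from Tables 14.2.2.7 to 14.2.2.9.

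The cost is SAP wording, programming and some table columns. No new data, visits or patients are needed.

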13. LISTING SHELLS

The following listing shells provide a framework for the display of data from this study. The shells may change due to unforeseen circumstances. These shells may not be reflective of every aspect of this study, but are intended to show the general layout of the listings that will be presented and included in the final report.

Note to programmer: Formatting and content of listings may be modified based on provided data.

Appendix 16.1.10.1 Clinical Laboratory Reference Ranges

Site	Laboratory Group	Test Name	Gender	Age Category	Reference Range	Unit
XXXXX	Serum Chemistry	Test Name	◇	◇	XX - XX	units
		Test Name	◇	◇	XX - XX	units
		Test Name	◇	◇	XX - XX	units
		Test Name	◇	◇	XX - XX	units
		Test Name	◇	◇	XX - XX	units
		Test Name	◇	◇	XX - XX	units
	Hematology	Test Name	◇	◇	XX - XX	units
		Test Name	◇	◇	XX - XX	units
		Test Name	◇	◇	XX - XX	units
		Test Name	◇	◇	XX - XX	units
		Test Name	◇	◇	XX - XX	units

<similar for remaining Laboratory Groups and Test Names>

Program: /AAXXXX/ECR/sas_prg/stsas/lis LIS_PROGRAMNAME.SAS DDMMYY YYYY HH:MM

